#### **Veliparib: PO**

Days: 1–5

Dose: 25 mg/m^2/dose BID (Total Daily Dose: 50 mg/m^2/day)

Veliparib will be given twice daily, and the morning (AM) dose should be given 60–120 minutes prior to the daily dose of temozolomide. Veliparib and temozolomide will be given on Days 1–5.

Alternatively, temozolomide may be given with the PM dose of veliparib, as long as:

- 1) temozolomide is given around the same time consistently every day
- 2) veliparib is administered 60-120 minutes prior to temozolomide to optimize the synergistic activity between the two agents.

Administer veliparib orally without regards to meals.

- Veliparib Oral Solution: Do not mix veliparib oral solution directly in apple/grape juice; however, patients can drink apple juice or grape juice after the dose. Do NOT drink orange juice, other citrus based juices, or grapefruit juice while taking veliparib oral solution (Days 1–5).
- Veliparib Capsules: Swallow capsules whole; do not chew or break.

For patients taking the oral solution, veliparib doses  $<$  30 mg should be rounded to the nearest 1 mg [0.1 mL] (e.g., 11.4 mg to be rounded to 11 mg and 19.5 mg to be rounded to 20 mg). For doses between 30 to 100 mg, round oral solution doses to the nearest 2 mg [0.2 mL] (e.g., 45.4 mg should be rounded to 46 mg).

Doses of capsule formulation should be rounded to the nearest 10 mg and can be divided unevenly if necessary to achieve a total daily dose (e.g., 30 mg in AM and 20 mg in PM). See suggested capsule dosing tables in [Appendix VII](#).

Patient veliparib wallet cards are provided in the [Appendix VI](#).

**Note:** Patients are not allowed to take a combination of capsules and the oral solution of veliparib for an individual dose.

If emesis occurs within 15 minutes of administration of veliparib, the dose should be repeated once. A missed dose will not be made up, but the missed dose and reason for missing the dose should be recorded in the patient's record.

**Temozolomide: PO**

Days: 1–5

Dose: 135 mg/m^2/dose once daily

Temozolomide should be administered 60-120 minutes after the veliparib dose and should be given consistently around the same time every day.

**Note:** Temozolomide doses should be rounded to the nearest 5 mg capsule size (see [Appendix VIII](#) for suggested capsule formulation dosing tables). For patients unable to swallow capsules, the capsules can be opened and mixed with apple sauce or apple juice, which should be used immediately after mixing (preferred) or must be used in 2 hours after mixing (see [Section 6.2](#) and [Appendix V](#)).

If emesis occurs within 15 minutes of taking a dose of temozolomide, then the dose may be repeated once. If emesis occurs after 15 minutes, the dose should not be repeated. Instructions for administration of oral temozolomide to young children are included in [Appendix V](#).

Disease evaluations should occur prior to every odd number of Maintenance cycle (see [Section 4.5.2](#)) for details).

See [Section 5.0](#) for Dose Modifications based on Toxicities.

Following completion of Cycle 1 of Maintenance chemotherapy, subsequent cycles will start on Day 29 or when criteria to begin the next cycle are met, whichever occurs later, absent disease progression or unacceptable toxicity.

**4.5 Maintenance Chemotherapy – Cycles 2–10**

**4.5.1 Therapy Delivery Map (TDM) – Maintenance Chemotherapy – Cycles 2–10**

Patients will receive up to 10 total cycles of Maintenance chemotherapy. Each cycle lasts 28 days. This TDM is for one cycle of Cycles 2–10. Please indicate the cycle # below.	_____ Patient COG ID number  _____ DOB
---	--

*Criteria to start Cycle 2 and subsequent cycles:* ANC  $\geq$  750/ $\mu$ L, platelets  $\geq$  75,000/ $\mu$ L (without transfusion within the last 7 days), serum creatinine  $\leq$  1.5 x ULN, total bilirubin  $\leq$  1.5 x ULN, ALT  $<$  2.5 x ULN, AST  $<$  2.5 x ULN, and no evidence of progressive disease as assessed clinically and/or by imaging. This TDM is two pages in length.

DRUG	ROUTE	DOSAGE	DAYS	IMPORTANT NOTES
Veliparib (IND # 139199)	PO	25 mg/m  /dose BID (see Appendix VII )	1–5	The morning dose of veliparib should be given 60–120 minutes prior to temozolomide. See Section 4.5.3 for dosing and administration instructions. Total Daily Dose: 50 mg/m  /day
Temozolomide (TEMO)	PO	135 mg/m  /dose once daily (see Appendix VIII )	1–5	

Cycle #: \_\_\_\_\_ Ht \_\_\_\_\_ cm Wt \_\_\_\_\_ kg BSA \_\_\_\_\_ m^2

Date Due	Date Given	Day	Veliparib (AM dose) mg	Veliparib (PM dose) mg	TEMO mg	Studies
Enter calculated dose above and actual dose administered below						
		1	mg	mg	mg	a–i
		2	mg	mg	mg	
		3	mg	mg	mg	
		4	mg	mg	mg	
		5	mg	mg	mg	
		8				d
		15				d
		21				d
		28	Subsequent cycles will start on Day 29 or when the criteria to begin the next cycle are met, whichever occurs later, absent disease progression or unacceptable toxicity.			

See [Section 5.0](#) for Dose Modifications for Toxicities and the COG Member website for Supportive Care Guidelines.

4.5.2 Required Observations in Maintenance Chemotherapy – Cycles 2–10

- a. Physical exam
- b. Height, weight
- c. Performance status: Prior to each odd-numbered cycle of Maintenance chemotherapy (e.g., Cycle 1, Cycle 3, Cycle 5, etc.)
- d. CBC/diff/platelets: Obtain weekly
- e. Bilirubin, Creatinine
- f. AST/ALT
- g. Brain MRI: Prior to each odd-numbered cycle of Maintenance chemotherapy (e.g., Cycle 3, Cycle 5, etc.)

**This listing only includes evaluations necessary to answer the primary and secondary aims. OBTAIN OTHER STUDIES AS REQUIRED FOR GOOD CLINICAL CARE.**

**Comments**

(Include any held doses, or dose modifications)

#### 4.5.3 Maintenance Chemotherapy Treatment Details – Cycles 2–10

Each cycle of Maintenance chemotherapy lasts 28 days.

*Criteria to start Cycle 2 and subsequent cycles:*

- Absolute neutrophil count (ANC)  $\geq$  750/ $\mu$ L
- Platelet Count  $\geq$  75,000/ $\mu$ L (without transfusion within the last 7 days)
- Serum creatinine  $\leq$  1.5 x ULN
- Total bilirubin  $\leq$  1.5 x ULN, ALT  $<$  2.5 x ULN, AST  $<$  2.5 x ULN
- The patient has no evidence of progressive disease (see [Section 10.4](#)) as assessed clinically and/or by imaging studies.

Disease evaluations should occur prior to every odd number of Maintenance cycle (see [Section 4.5.2](#)) for details).

##### **Veliparib: PO**

Days: 1–5

Dose: 25 mg/m^2/dose BID (Total Daily Dose: 50 mg/m^2/day)

Veliparib will be given twice daily, and the morning (AM) dose should be given 60–120 minutes prior to the daily dose of temozolomide. Veliparib and temozolomide will be given on Days 1–5.

Alternatively, temozolomide may be given with the PM dose of veliparib, as long as:

- 1) temozolomide is given around the same time consistently every day
- 2) veliparib is administered 60–120 minutes prior to temozolomide to optimize the synergistic activity between the two agents.

Administer veliparib orally without regards to meals.

- Veliparib Oral Solution: Do not mix veliparib oral solution directly in apple or grape juice; however, patients can drink apple juice or grape juice after the dose. Do NOT drink orange juice, other citrus based juices, or grapefruit juice while taking veliparib oral solution (Days 1-5 of each cycle).
- Veliparib Capsules: Swallow capsules whole; do not chew or break.

For patients taking the oral solution, veliparib doses  $<$  30 mg should be rounded to the nearest 1 mg [0.1 mL] (e.g., 11.4 mg to be rounded to 11 mg and 19.5 mg to be rounded to 20 mg). For doses between 30 to 100 mg, round oral solution doses to the nearest 2 mg [0.2 mL] (e.g., 45.4 mg should be rounded to 46 mg).

Doses of capsule formulation should be rounded to the nearest 10 mg and can be divided unevenly if necessary to achieve a total daily dose (e.g., 30 mg in AM and 20 mg in PM). See suggested capsule dosing tables in [Appendix VII](#).

Patient veliparib wallet cards are provided in the [Appendix VI](#).

**Note:** Patients are not allowed to take a combination of capsules and the oral solution of veliparib for an individual dose.

If emesis occurs within 15 minutes of administration of veliparib, the dose should be repeated once. A missed dose will not be made up, but the missed dose and reason for missing the dose should be recorded in the patient's record.

**Temozolomide: PO**

Days: 1-5

Dose: 135 mg/m^2/dose once daily

Temozolomide should be administered 60-120 minutes after the veliparib dose and should be given consistently around the same time every day.

**Note:** Temozolomide doses should be rounded to the nearest 5 mg capsule size (see [Appendix VIII](#) for suggested capsule formation dosing tables). For patients unable to swallow capsules, the capsules can be opened and mixed with apple sauce or juice, which should be used immediately after mixing (preferred) or must be used in 2 hours after mixing (see [Section 6.2](#) and [Appendix V](#)).

If emesis occurs within 15 minutes of taking a dose of temozolomide, then the dose may be repeated once. If emesis occurs after 15 minutes, the dose should not be repeated. Instructions for administration of oral temozolomide to young children are included in [Appendix V](#).

See [Section 5.0](#) for Dose Modifications based on Toxicities.

Following completion of this cycle of Maintenance chemotherapy, subsequent cycles will start on Day 29 or when criteria to begin the next cycle are met, whichever occurs later, absent disease progression or unacceptable toxicity. Patients may continue for up to 10 cycles.

## 5.0 DOSE MODIFICATIONS FOR TOXICITIES

### 5.1 Dose Levels Tables

The starting dose level of veliparib is 65 mg/m^2/dose BID during Chemoradiotherapy and 25 mg/m^2/dose BID during Maintenance therapy.

**Table 1.** Dose Levels for Veliparib during Chemoradiotherapy

Dose Level	Veliparib dose (mg/m  /dose BID)
-2	35 mg/m  /dose BID
-1	50 mg/m  /dose BID
1*	65 mg/m^2/dose BID

\*Starting dose level

**Table 2.** Dose Levels for Veliparib and Temozolomide during Maintenance Therapy

Dose Level	Veliparib Dose	Temozolomide Dose
-1	20 mg/m  /dose BID	135 mg/m  /day
1*	25 mg/m^2/dose BID	135 mg/m^2/day

\*Starting dose level

### 5.2 Dose Modifications for Veliparib during Chemoradiotherapy

#### 5.2.1 Hematological Toxicities

**Note: Radiation therapy should not be interrupted unless clinically indicated.**

##### 5.2.1.1 Definition of Dose-Modifying Toxicity

Dose modifying toxicities will be defined as any of the following events that are at least possibly related to veliparib therapy.

- Platelets < 50,000/μL (thrombocytopenia ≥ Grade 3) requiring transfusions on ≥ 2 separate days within a 7-day period
- Platelets < 25,000/μL (thrombocytopenia Grade 4)
- ANC < 500/μL (neutropenia Grade 4)

##### 5.2.1.2 Dose Modifications for Hematologic Toxicities

##### 5.2.1.2.1 **If a patient experiences dose-modifying thrombocytopenia (platelets < 50,000/μL requiring transfusions on ≥ 2 separate days within a 7-day period OR platelets < 25,000/μL):**

Hold veliparib. Obtain twice weekly CBC until platelets ≥ 75,000/μL. Platelet transfusion is permissible and strongly encouraged for patients with platelets < 50,000/μL to minimize the risk of intra-tumoral hemorrhage.

- For patients on Dose Level 1 or Dose Level -1: Veliparib should be restarted at one dose lower (Table 1) once platelets recover to ≥ 75,000/μL (transfusion

independent). If platelet count is  $< 75,000/\mu\text{L}$  after withholding veliparib for  $> 14$  days, veliparib during Chemoradiotherapy should be discontinued and restarted at the time of Maintenance chemotherapy at the starting dose level for Maintenance chemotherapy (Table 2).

- For patients on Dose Level -2: Veliparib during Chemoradiotherapy should be discontinued and restarted at the time of Maintenance chemotherapy at the starting dose level for Maintenance chemotherapy (Table 2).

#### 5.2.1.2.2 **If a patient experiences dose-modifying neutropenia (ANC $< 500/\mu\text{L}$ ):**

Hold veliparib. Obtain twice weekly CBC until ANC  $> 750/\mu\text{L}$ . Patients may receive filgrastim (G-CSF) or biosimilar support at the discretion of the treating physician. If G-CSF is utilized, ANC determination for restart of veliparib must be after  $> 48$  hours without G-CSF support.

- For patients on Dose Level 1 or Dose Level -1: Veliparib should be restarted at one dose level lower (Table 1) once ANC recovers to  $\geq 750/\mu\text{L}$ . If ANC  $< 500/\mu\text{L}$  after withholding veliparib for  $> 14$  days, veliparib during Chemoradiotherapy should be discontinued and restarted at the time of Maintenance chemotherapy at the starting dose level for Maintenance chemotherapy (Table 2).
- For patients on Dose Level -2: Veliparib during Chemoradiotherapy should be discontinued and restarted at the time of Maintenance chemotherapy at the starting dose level for Maintenance chemotherapy (Table 2).

### 5.2.2 Non-Hematological Toxicities

#### 5.2.2.1 Definition of Dose-Modifying Toxicity (DMT)

- Any Grade 4 non-hematologic toxicity that is at least possibly related to veliparib.
- Any Grade 3 non-hematologic toxicity that is at least possibly related to veliparib, and is considered medically significant or sufficiently intolerable by patients requiring treatment interruption, with the exception of:
  - Grade 3 nausea and vomiting of  $< 7$  days
  - Grade 3 elevation of transaminases that returns to levels meeting eligibility criteria within 7 days of study drug interruption and does not recur upon restarting drug
  - Grade 3 fever or infection of  $< 5$  days in duration
  - Grade 3 hypophosphatemia, hypokalemia, hypocalcemia or hypomagnesemia responsive to supplementation

### 5.2.2.2 Dose Modifications for Non-Hematological Toxicities

**Note: Radiation therapy should not be interrupted unless clinically indicated.**

If any dose-modifying non-hematological toxicity as defined in [Section 5.2.2.1](#) occurs that is at least possibly related to veliparib, hold veliparib. Restart veliparib at one dose level lower (Table 1) if the toxicity resolves to meet eligibility criteria (see [Section 3.3.4](#)) within 14 days. If the toxicity does resolve to meet eligibility criteria within 14 days, or if the patient is already on Dose Level -2, veliparib should be discontinued for the remainder of Chemoradiotherapy, but should be restarted at maintenance chemotherapy at the starting dose level for Maintenance chemotherapy (Table 2).

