#### 4.1.1 Chemoradiotherapy

Prior to beginning protocol therapy, obtain biology samples for patients who have provided consent. See [Section 15.2](#) for details.

During radiation, patients will receive veliparib throughout RT as outlined below at 65 mg/m^2/dose PO BID x 5 days per week (typically Monday–Friday) concurrent with each day of RT. **If circumstances require, starting veliparib may be delayed up to 3 days if necessary, but veliparib must start no later than Day 34 after surgery and no later than the 4th day of RT (see [Section 8.2](#)).** If timing permits, the morning (AM) dose of veliparib should be given 60–120 minutes prior to daily RT. A missed dose of veliparib should not be made up, and veliparib will finish on the last day of RT.

RT will be given over 6–7 weeks during this course (see [Section 17.0](#)). The goal of treatment planning and dose prescription is that the dose to the International Commission on Radiation Units and Measurements (ICRU) reference point shall be 54 Gy given over 6 weeks. For patients whose tumors have not been completely resected and residual disease remains, the dose will be boosted to a total dose of 59.4 Gy (an additional 5.4 Gy boost). RT will be given in standard fractions. RT will be administered to a dose of 54 Gy in 30 daily fractions (or 59.4 Gy in 33 daily fractions if appropriate), treating 5 days per week (e.g., Monday–Friday) as outlined in [Section 17.0](#). RT will not be interrupted for veliparib related toxicities (see [Section 5.0](#)), unless clinically indicated.

Chemoradiotherapy Phase									
Week	1	2	3	4	5	6	7	Week 7–10	
Veliparib, BID	Twice daily, Monday–Friday, for 6–7 weeks (AM dose should be given 60-120 minutes before RT)							Rest/Evaluation	
Radiation Therapy	Daily, Monday–Friday for 6–7 weeks								

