#### 5.3.2.2 Dose Modifications for Non-Hematological Toxicities

For dose-modifying non-hematologic toxicities listed above that occur during Maintenance chemotherapy, veliparib and temozolomide will be withheld until the toxicity resolves to meet on eligibility criteria (see [Section 3.3.4](#)), and the patient will restart veliparib and temozolomide at Dose Level -1 (Table 2). Protocol therapy will be discontinued if a non-hematologic dose modifying toxicity occurs at Dose Level -1.

Patients who experience a dose-modifying non-hematological toxicity that does not resolve to meet eligibility or baseline parameters within 21 days after the planned start of the next treatment cycle (i.e., by Day 49) must be removed from protocol therapy.

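### Section 5.2.2.2 tells sites both to restart and to stop veliparib when a non-haematological toxicity resolves within 14 days, because a "not" appears to be missing

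*Combined protocol and SAP*

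**What the plan says.** Section 5.2.2.2 covers dose-modifying non-haematological toxicity that is at least possibly related to veliparib during chemoradiotherapy. Veliparib is held, and two consecutive sentences then say what happens next.

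- First sentence: "Restart veliparib at one dose level lower (Table 1) if the toxicity resolves to meet eligibility criteria", with a limit of 14 days.
- Second sentence: "If the toxicity does resolve to meet eligibility criteria within 14 days, or if the patient is already on Dose Level -2", then "veliparib should be discontinued for the remainder of Chemoradiotherapy, but should be restarted at maintenance chemotherapy", at the Maintenance starting dose level.

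Three other sections bear on how to read this.

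- Section 5.2.1.2.1 (thrombocytopenia, same treatment phase, Levels 1 and -1): restart one level lower once platelets recover to at least 75,000/µL. If they are still below that after more than 14 days of withholding, "veliparib during Chemoradiotherapy should be discontinued and restarted at the time of Maintenance chemotherapy at the starting dose level".
- Section 5.2.1.2.2 (neutropenia, same phase, Levels 1 and -1): "Veliparib should be restarted at one dose level lower (Table 1) once ANC recovers" to at least 750/µL. Stopping applies if the ANC is below 500/µL after more than 14 days of withholding.
- Section 5.3.2.2 (non-haematological toxicity in Maintenance): "Patients who experience a dose-modifying non-hematological toxicity that does not resolve to meet eligibility or baseline parameters within 21 days" of the planned start of the next cycle come off protocol therapy.

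Section 4.1.1 adds: "A missed dose of veliparib should not be made up, and veliparib will finish on the last day of RT".

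**The concern.** The two sentences share the same criterion and the same 14-day window, yet the first orders a restart and the second a stop. A site cannot obey both. Taken literally, the second sentence also leaves the first with no patient to apply to. The opposite case, a toxicity not resolved by day 14 on Level 1 or -1, is left without any explicit instruction.

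What is at stake is exposure to the study drug during radiotherapy. A site that acts on the second sentence stops veliparib in a patient who has recovered and should resume at a lower dose. Because missed doses are not made up and veliparib ends with RT, the loss is permanent. If sites read the rule differently, exposure would differ between sites for reasons unrelated to the patients. Under Section 9.4, anyone who starts RT and takes one veliparib dose is evaluable for efficacy, so an under-exposed patient stays in the EFS analysis. The risk is under-dosing. It is not dosing through toxicity, since an unresolved patient remains on hold.

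**Working it through.** **Logic of the text.** The table sets the printed rule beside the same rule with *not* inserted in the second sentence.

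| Patient's situation | As printed | With *not* inserted |
|---|---|---|
| Level 1 or -1, resolved within 14 days | Restart one level lower (first sentence) and stop for the rest of chemoradiotherapy (second sentence) | Restart one level lower |
| Level 1 or -1, not resolved within 14 days | Hold only; no further instruction | Stop for the rest of chemoradiotherapy |
| Level -2 | Stop by the explicit Level -2 clause; Table 1 has no lower level | Stop |

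Inserting the word removes both the contradiction and the gap. It also brings the rule into line with Sections 5.2.1.2.1, 5.2.1.2.2 and 5.3.2.2, all of which attach stopping or removal to failure to recover. The affected sentence is current protocol text. The summary of changes lists no revision to Section 5.2.2.2, and no other section corrects it.

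**Size of the dose loss for one affected patient.** The plan gives no figure to reproduce, so these are worked examples.

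Inputs from the documents:
- 30 RT days, or 33 with the boost, with veliparib twice daily on RT days only (Sections 4.1.1 and 4.3.1).
- Table 1 doses: Level 1 = 65, Level -1 = 50 and Level -2 = 35 mg/m² per dose.

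Assumptions:
- Veliparib starts on RT day 1 at Level 1.
- There are five fractions a week without breaks, so a 14-day hold covers 10 RT days and a 7-day hold covers 5.
- The day the hold starts and its length are chosen for illustration.

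Planned cumulative dose at Level 1:
- 30 fractions: 30 × 2 × 65 = 3,900 mg/m² (60 doses).
- 33 fractions: 33 × 2 × 65 = 4,290 mg/m² (66 doses).

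Doses forfeited by not restarting = 2 × (N − f − h + 1), where N is the number of RT days, f the first held RT day and h the number of RT days held. Each forfeited dose would have been 50 mg/m², because the correct action is to restart at Level -1.

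| N | f | h | Restart day forgone | Doses forfeited | mg/m² forfeited | Share of plan |
|---|---|---|---|---|---|---|
| 30 | 11 | 10 | 21 | 2 × 10 = 20 | 20 × 50 = 1,000 | 1,000/3,900 = 25.6% |
| 33 | 11 | 10 | 21 | 2 × 13 = 26 | 26 × 50 = 1,300 | 1,300/4,290 = 30.3% |
| 30 | 6 | 5 | 11 | 2 × 20 = 40 | 40 × 50 = 2,000 | 2,000/3,900 = 51.3% |
| 30 | 20 | 10 | 30 | 2 × 1 = 2 | 2 × 50 = 100 | 100/3,900 = 2.6% |

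These rows are not bounds. An earlier or shorter hold forfeits more. With 30 fractions, a 14-day hold that starts on RT day 21 or later leaves nothing to forfeit.

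**The case against.** The strongest reply is that context corrects the error. The first sentence is clear, the Level -2 clause makes sense only as the alternative to restarting, and the two haematological rules just above have the same restart-or-stop structure. A careful site would supply the missing word, and the documents report no misapplication. This is fair as a statement about likelihood, and it means that variation between sites is a possibility, not something shown. It does not make the printed order correct. Sites are sent to Section 5.0 for dose modifications, and a dosing rule should not depend on readers overruling it.

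Second, the missing instruction at day 14 has little practical effect. Restart is conditional on resolution within 14 days, so an unresolved patient has no route back to veliparib before RT ends. That is largely right. What remains is that a patient who recovers on day 17, say, has no explicit rule.

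Third, the parallels are not exact. The neutropenia rule restarts at an ANC of 750/µL but stops only below 500/µL, which leaves the interval between them unaddressed. The Maintenance rule has a different window and a different consequence. Both points are correct, but every one of these rules still ties stopping to non-recovery, which is the feature that matters here.

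Fourth, few patients can be affected. The event must be Grade 3 or 4, at least possibly veliparib-related, outside the listed exceptions and resolved within 14 days, in a patient on Level 1 or -1. Only Stratum 2, with 30 planned patients, is still open. This stands, and it limits the impact.

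**Conclusion.** The concern holds. For patients on Dose Level 1 or -1, Section 5.2.2.2 as printed orders both a restart and a stop on the same condition, and it leaves the unresolved case without an explicit stop. Level -2 is unaffected. That a *not* was dropped is an inference, but the parallel rules and the structure of the sentence leave no other sensible reading.

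The possible harm is lost veliparib exposure during RT in recovered patients: about 26% to 30% of the planned cumulative dose in the day-11 example, and more or less with other timing. Those percentages rest on assumed onset and hold length, and the frequency of qualifying events is not in the documents. Maintenance starts at the usual starting level under either reading. Sample size, type I error and power do not change. The sentence should be corrected because it is an operative dosing instruction that is wrong as written.

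**What to change.** In the second sentence of the rule in Section 5.2.2.2, insert *not* between *does* and *resolve*, so that stopping for the remainder of chemoradiotherapy applies when the toxicity does not resolve to eligibility criteria within 14 days, or when the patient is already on Dose Level -2. Leave the rest of the sentence as it is. Each situation then has one action, and patients unresolved at day 14 have an explicit stop. Tell sites of the correction when it is issued.

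The cost is one word in the next amendment and a site notice. No design element, analysis or data collection needs to change.
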